6.5.1 MSQoL

The MSQoL consists of 14 items across the following 3 domains: (1) restrictive role function, (2) preventative role function and (3) emotional function.

Descriptive Analyses

The table of values and changes from baseline in scores is provided by treatment group and overall for each domain for the DBT efficacy analysis set at the following time points: baseline; Week 12 of the DBT outcomes research analysis period; Week 24 and Week 52 in the OL rimegepant outcomes research analysis period. Results for overall are displayed only at baseline and time points in the OL rimegepant outcomes research analysis period. Results support exploratory objective #8.

The frequency table of MSQoL domain score reduction from baseline categories is provided by treatment group and overall for the DBT efficacy analysis set at the following time points: Week 12 of the DBT outcomes research analysis period; Week 24 and Week 52 in the OL rimegepant outcomes research analysis period. Results for overall are displayed only at time points in the OL rimegepant outcomes research analysis period.

Treatment Group Comparisons

Analyses of each domain are based on the DBT efficacy analysis set with paired data, i.e., nonmissing domain scores at both baseline and Week 12 of the DBT outcomes research analysis period.

For each domain, treatment groups are compared using a linear regression model with the following attributes:

- Variables: Week 12 change from baseline in the score as the dependent variable; baseline score as a covariate; treatment group and randomization stratum as fixed effects.
- SE estimation method: See Section 6.3.1.1..

The table provides n (i.e., number of subjects with paired data) and the following model estimates for each domain:

- LSM change from baseline at Week 12, SE, and 95% CI for each treatment group
- Difference in LSM changes from baseline at Week 12 between each rimegepant treatment group and placebo (rimegepant placebo), SE, 95% CI, and p-value.

Results for the restrictive role function support secondary objective #5, whereas results for the other domains support exploratory objective #8.

See Section 9.3.2 for example SAS code. Model estimates by randomization stratum (yes, no) are presented in the same table, using additional linear regression models that exclude randomization stratum as a fixed effect.

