- For safety objectives, study drug discontinuation is handled with a "while-on-treatment strategy". All observed values of the endpoint of interest are used on or before study drug discontinuation + 7 days (see Section 7.2 and the Core SAP).
- For outcomes research, study drug discontinuation is handled with a "treatment policy strategy", i.e., the occurrence of the intercurrent event is considered irrelevant. All observed values of the endpoint of interest are used regardless of study drug discontinuation.

Non-study prophylactic migraine medication use before the time point of interest defining the endpoint is considered an intercurrent event. For all objectives, this intercurrent event is handled with a treatment policy strategy; all observed values of the endpoint of interest are used.

Nonstudy acute migraine-specific medication use before the time point of interest defining the endpoint is also considered an intercurrent event, except for efficacy objectives based on acute migraine-specific medication days or acute migraine medication days.

- For efficacy objectives based on migraine days or headache days, this intercurrent event is handled with a composite strategy, such that acute migraine-specific medication use is part of the endpoint definition of migraine days and headache days.
- For safety and outcomes research objectives, this intercurrent event is handled with a treatment policy strategy, such that all observed values of the endpoint of interest are used.

Use of nonstudy other medication to treat headache (migraine or nonmigraine) or aura before the time point of interest defining the endpoint is also considered an intercurrent event, except for the efficacy objective based on acute migraine medication days.

- For efficacy objectives based on headache days, this intercurrent event is handled with a composite strategy, such that medication use is part of the endpoint definition of headache days.
- For all other efficacy, safety, and outcomes research objectives, this intercurrent event is handled with a treatment policy strategy, such that all observed values of the endpoint of interest are used.

See Section 4.1 for analysis sets that are used to assess endpoints.

Data Sources for Endpoints

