	Use of nonstudy other medication to treat headache (migraine or nonmigraine) or aura: treatment policy strategy
Objective 4	Mean number of acute migraine-specific medication days per month in the last 4 Weeks of the DBT Phase

Efficacy Endpoint	Mean number of acute-migraine-specific days per month in the last 4 weeks (Weeks 9 to 12) of the DBT Phase
Summary	Value by treatment group using descriptive statistics and linear mixed effects model with repeated measures, and difference between treatment groups from the model for the DBT migraine analysis set
Intercurrent Events	Study drug discontinuation: hypothetical strategy
	Non-study prophylactic migraine medication use: treatment policy strategy
	Nonstudy acute migraine-specific medication use: not applicable
	Use of nonstudy other medication to treat headache (migraine or nonmigraine) or aura: treatment policy strategy
Objective 5	Mean change from baseline in the MSQoL restrictive role function domain score at Week 12 of the DBT Phase
Outcomes Research Endpoint	Mean change from baseline in the MSQoL restrictive role function domain score at Week 12 of the DBT Phase
Summary	Change from baseline by treatment group using descriptive statistics and linear regression models, and difference between treatment groups from the model for the DBT efficacy analysis set
Intercurrent Events	Study drug discontinuation: treatment policy strategy
	Non-study prophylactic migraine medication use: treatment policy strategy
	Nonstudy acute migraine-specific medication use: treatment policy strategy
	Use of nonstudy other medication to treat headache (migraine or nonmigraine) or aura:
	treatment policy strategy
Objective 6	Mean change from baseline in the MIDAS total score at Week 12 of the DBT Phase
Objective 6 Outcomes Research Endpoint	Mean change from baseline in the MIDAS total score at Week 12 of the DBT Phase Mean change from baseline in the MIDAS total score at Week 12 of the DBT Phase
Objective 6 Outcomes Research Endpoint Summary	Mean change from baseline in the MIDAS total score at Week 12 of the DBT Phase Mean change from baseline in the MIDAS total score at Week 12 of the DBT Phase Change from baseline by treatment group using descriptive statistics and linear regression models, and difference between treatment groups from the model for the DBT efficacy analysis set

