5 SAMPLE SIZE, POWER, AND TYPE I ERROR

The study randomizes approximately 245 subjects per treatment arm to obtain roughly 225 evaluable subjects per treatment arm.

With a sample size of roughly 490 subjects randomized, and 245 subjects per group, we expect roughly 225 evaluable subjects per group in the efficacy data set. Assuming rimegepant provides roughly a 1 day advantage over placebo on the primary endpoint, a common standard deviation of 3.75 days, and a 2-sided alpha level of 0.05, then the study will have roughly 80% power on the primary endpoint. The estimates for the change in migraine days per month and the standard deviation are consistent with publicly available information from another investigational oral CGRP antagonist for this indication.

Type I error will be controlled by using a hierarchical gate keeping procedure. If the primary endpoint is significant at the 2-sided alpha level of 0.05, then secondary efficacy or outcomes research endpoints are tested hierarchically, each at a 2-sided alpha level of 0.05, in the order in which they appear in Section 3.2.2. Thus, a secondary efficacy or outcomes research endpoint is tested only if the preceding secondary endpoint in the hierarchy is determined to be significant (i.e., p-value ≤ 0.05). If a test in the hierarchy is not significant, then any further tests on endpoints in the sequence have p-values presented only for descriptive purposes, and no conclusions are drawn from those results. Note that secondary safety endpoints are not tested.

For exploratory endpoints, no attempt is made to adjust for multiplicity. Any exploratory endpoints for which p-values are produced are evaluated at an unadjusted, 2-sided alpha level of 0.05 and presented only for descriptive purposes.

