If the primary endpoint is significant, then the secondary efficacy and outcomes research endpoints are tested hierarchically, each at a 2-sided alpha level of 0.05, in the order specified in Section 3.2.2. Thus, a secondary efficacy or outcomes research endpoint is tested only if the preceding secondary endpoint in the hierarchy is determined to be significant (i.e., p-value \leq 0.05). If a test in the hierarchy is not significant, then any further tests on endpoints in the sequence have p-values presented only for descriptive purposes, and no conclusions are drawn from those results.

For a given treatment comparison of a continuous endpoint, the null hypothesis of interest H₀ is that the mean change observed on rimegepant (denoted $\mu_{rimegepant}$) is equal to the one observed on placebo (denoted $\mu_{placebo}$), i.e., H₀: $\mu_{rimegepant} = \mu_{placebo}$. The alternative 2-sided hypothesis of interest H₁ is that the mean changes observed on rimegepant and placebo differ, i.e., H₁: $\mu_{rimegepant} \neq \mu_{placebo}$. For a given treatment comparison of a binary endpoint, the hypotheses are based on percentages instead of mean changes.

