6.5 Outcomes Research

Analyses are based on as-randomized treatment group for the DBT efficacy analysis sets.

Outcomes research questionnaires MSQoL, MIDAS, and EQ-5D-5L are assessed using the eDiary at Baseline, Week 12, Week 24, and Week 52.

Measurements are slotted into analysis periods and analysis visits using the eDiary finding date and the following steps:

- 1) Measurements are slotted into the pretreatment, DBT outcomes research, and OL rimegepant outcomes research analysis periods.
- 2) Measurements are slotted into analysis visits in the analysis periods listed in the previous step (see Table 5).

Refer also to the Core SAP for details about measurement slotting. See Sections 6.2.5, 7.2, and 7.3 for definitions of baseline, analysis periods, and analysis visit windows, respectively.

By-subject listings of outcomes research questionnaires (i.e., MSQoL, MIDAS, and EQ-5D-5L) are provided for the enrolled analysis set. The listing displays values and changes from baseline for the following: MSQoL domain scores; MIDAS total, absenteeism, and presenteeism scores; EQ-5D-5L VAS score.

Refer to the Core SAP for the following: detailed descriptions of these questionnaires and rating scales; calculating scores and imputing missing data; deriving categories; handling multiple questionnaires or rating scale values in an analysis visit window or on the same assessment date; and TLF contents.

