6.5.2 MIDAS

The MIDAS is a retrospective, patient-administered, 5-item questionnaire that measures headache-related disability as lost time due to headache from paid work or school, household work, and non-work activities.

Descriptive Analyses

The table of values and changes from baseline in total, absenteeism, presenteeism, and item scores is provided, and has a similar format as the one described in Section 6.5.1.

Results support exploratory objective #8.

Treatment Group Comparisons

Analyses of each score (total, absenteeism, presenteeism) are based on the DBT efficacy analysis set with scores at both baseline and Week 12 of the DBT outcomes research analysis period.

For each score, treatment groups are compared using a linear regression model with the same attributes as the one described in Section 6.5.1. The table has the same format.

Results for the total score support secondary objective #6, whereas results for the other scores support exploratory objective #8.

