6.5.3 EQ-5D-5L

The EQ-5D-5L is a 2-part assessment questionnaire of the subject's current health. In the first part, subjects rate their current level of function in 5 dimensions: mobility, self-care, usual activities, pain/discomfort, and anxiety/depression. In the second part, subjects rate their health on a VAS scale from 0 (worst imaginable health) to 100 (best imaginable health).

Descriptive Analyses

The table of values and changes from baseline in the VAS and utility index scores is provided, and has a similar format as the one described in Section 6.5.1. The utility index score is calculated from the official Japanese tariff based on time trade-off data.³

The frequency table of EQ-5D-5L dimension function level is provided by treatment group and overall for the DBT efficacy analysis set at the following time points: baseline; Week 12 of the DBT outcomes research analysis period; Week 24 and Week 52 of the OL rimegepant outcomes research analysis period. Results for overall are displayed only at baseline and time points in the OL rimegepant outcomes research analysis period.

Results support exploratory objective #8.

Treatment Group Comparisons

Analyses are based on the DBT efficacy analysis set with VAS scores at both baseline and Week 12 of the DBT outcomes research analysis period.

Treatment groups are compared using a linear regression model with the same attributes as the one described in Section 6.5.1. The table has the same format.

Results support secondary objective #7.

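### Three alpha-controlled Week 12 questionnaire endpoints carry a treatment-policy label but are analysed only where a Week 12 score was observed, and the study SAP neither states nor checks the assumption this requires

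*SAP*

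**What the plan says.** All references are to the SAP, which covers C4951021 (migraine prevention). The supplied protocol is for C4951022, a single-dose acute study with none of these endpoints, so the point rests on the SAP alone.

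- **Testing.** Under Section 5, if the primary endpoint is significant, "then secondary efficacy or outcomes research endpoints are tested hierarchically, each at a 2-sided alpha level of 0.05". Section 6.3.2.3 adds that "a secondary efficacy or outcomes research endpoint is tested only if the preceding secondary endpoint in the hierarchy is determined to be significant". Objectives 5, 6 and 7 are the last three tests in the sequence.
- **Estimand.** Table 2 (Section 3.2.2) gives "Study drug discontinuation: treatment policy strategy" for each of the three endpoints and names the DBT efficacy analysis set as the basis. Section 3.2 explains the strategy for outcomes research: "All observed values of the endpoint of interest are used regardless of study drug discontinuation".
- **Analysis.** For MSQoL, "Analyses of each domain are based on the DBT efficacy analysis set with paired data" (6.5.1). For MIDAS, the analyses "are based on the DBT efficacy analysis set with scores at both baseline and Week 12 of the DBT outcomes research analysis period" (6.5.2). For EQ-5D-5L, "Analyses are based on the DBT efficacy analysis set with VAS scores at both baseline and Week 12" (6.5.3). Each is a single linear regression of Week 12 change on baseline score, treatment and stratum (6.5.1, code in 9.3.2).
- **Collection.** The questionnaires "are assessed using the eDiary at Baseline, Week 12, Week 24, and Week 52" (6.5). Section 2.1 sends subjects who leave the double-blind phase early to an end-of-treatment (EOT) visit in place of Week 12. Table 5 (7.3) sets the Week 12 window at study days 71 to 91.
- **Missing data.** The default is observed data (6.1.3). Jump-to-reference and tipping-point analyses are specified in 6.3.1.1 for the primary endpoint only. Section 6.5 refers to the Core SAP for questionnaire scoring and imputation.

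**The concern.** A treatment-policy estimand targets the effect in all subjects in the analysis population, whether or not they stay on drug. Using every observed value delivers that only if values are collected after discontinuation. Here there is one post-baseline time point in the double-blind phase, and the study SAP describes no Week 12 collection for subjects who have already left it. A stopper without a score in days 71 to 91 contributes nothing to the test.

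What is at stake is the meaning of three potentially significant secondary results. If rimegepant subjects who stop early do worse than those who stay, the paired-data estimate exceeds the treatment-policy effect, and a borderline result could be reported as a treatment-policy benefit that the full population would not support.

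**Working it through.** **1. The plan's own figure.** The only power statement is for the primary endpoint: 225 evaluable per arm, difference 1 day, SD 3.75, two-sided alpha 0.05 (Section 5). The expected z is (1/3.75) × √(225/2) = 0.2667 × 10.607 = 2.83, and the power is Φ(2.83 − 1.96) = 80.7%. This reproduces the stated figure of roughly 80% and is not in dispute. The SAP gives no SD, power or missing rate for the three questionnaire scores.

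**2. What the regression assumes.** Section 3.2 describes the hypothetical strategy as supposing that discontinuers would have responded like subjects of the same arm and stratum who did not discontinue. A paired-data regression on baseline score, treatment and stratum recovers the full-population effect only if, given those three variables, unobserved subjects would have scored like observed ones. For stoppers without a score, that is nearly the same supposition, yet Table 2 labels it treatment policy.

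**3. Who is likely to be unobserved.** If a subject leaves early and completes a questionnaire at an EOT visit on, say, day 50, Table 5 slots it to Week 8 (days 43 to 70), and none of the three analyses uses Week 8. A subject who is off drug but scored within days 71 to 91 is included.

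**4. Illustrative size.** Let m be the fraction of rimegepant subjects without a Week 12 score and D the observed-score difference. Assume that:
- missing rimegepant subjects have the placebo outcome;
- missing placebo subjects resemble observed placebo subjects;
- the standard error is unchanged.

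The treatment-policy difference is then (1 − m)D, the overstatement is 1/(1 − m) − 1, and z becomes z(1 − m).

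The documents give no value for m. The assumed range borrows two planning figures: 1 − 225/245 = 8.2% (primary evaluability, Section 5) and 1 − 400/490 = 18.4% (expected subjects not entering the open-label extension, Section 2.1). The second is a loose outer bound. Rounded to 8% and 18%, with 12% as an intermediate value:

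| m | Overstatement | z = 2.10 (p = 0.036) becomes | Observed z that would lose significance |
|---|---|---|---|
| 8% | 1/0.92 − 1 = 8.7% | 1.93 (p = 0.053) | 1.96 to 1.96/0.92 = 2.13 |
| 12% | 1/0.88 − 1 = 13.6% | 1.85 (p = 0.065) | 1.96 to 1.96/0.88 = 2.23 |
| 18% | 1/0.82 − 1 = 22.0% | 1.72 (p = 0.085) | 1.96 to 1.96/0.82 = 2.39 |

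The value z = 2.10 was chosen as a borderline case. Above the upper limits in the last column, the conclusion survives even full reversion to placebo.

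**The case against.** Several objections have force.

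- **Unseen documents.** The Core SAP is cited for imputing missing questionnaire data and defines the outcomes analysis periods, and the C4951021 protocol holds the assessment schedule. Off-drug follow-up may be described there. The revision history also records that EOT results were removed from the outcomes tables, which suggests that such scores may have been collected. This stands as a limit on how many stoppers are unobserved. It does not remove the requirement in 6.5.1 to 6.5.3 for scores at both visits, and an EOT score before day 71 is not a Week 12 score.
- **A reader might call this a completer analysis.** The documents do not support that. Scores are slotted by eDiary date, not by completion status, so off-drug subjects scored in the window count. It is an observed-score analysis.
- **A reader might infer that the estimates are biased in favour of rimegepant.** That is not shown. The regression is unbiased if missingness depends only on arm, baseline score and stratum. If placebo stoppers are the worse-off ones, the error could run the other way.
- **A reader might take 8% to 18% as the expected loss.** Neither figure is a missing rate for these scores. The 8% can include untreated subjects, who are outside the DBT efficacy set, and subjects with too few diary days. It can also be too low, because one usable month qualifies a subject for the migraine set. Entry to the extension is optional and conditional, so some who do not enter will have Week 12 scores.
- **Limited reach.** These tests are reached only if the primary endpoint and secondary endpoints 1 to 4 all succeed. The other secondary endpoints have no separately specified sensitivity analysis either, and the number of subjects with paired data is reported. All true, but that number alone does not show whether the result depends on the missing subjects.

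**Conclusion.** The concern holds in this form: for secondary objectives 5 to 7, the stated estimand and the planned analysis agree only under a missing-data assumption that the study SAP neither states nor checks for these endpoints. Following the plan can therefore produce an estimate that does not match its treatment-policy label. Under the illustrative assumptions above, the overstatement is about 9% to 22%, and only borderline results would change. That size rests on an assumed missing fraction and on full reversion of missing rimegepant subjects to placebo. Neither comes from the documents as a fact about these scores. The primary result and its power are unaffected.

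**What to change.** In SAP Section 6.5, before unblinding:

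1. State the missing-data assumption of the paired-data regression, and say that it supports a treatment-policy claim only under that assumption.
2. Add a sensitivity analysis of the three endpoints in DBT efficacy set subjects with a baseline score. Impute missing Week 12 change by the jump-to-reference approach of 6.3.1.1, adapted to one post-baseline time point and with the baseline questionnaire score in the imputation model. Report it beside the paired-data result, with the number lacking a Week 12 score by arm.
3. Describe a significant result as a treatment-policy effect only if the sensitivity analysis is consistent with it.

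Items 1 and 3 are needed because a sensitivity analysis alone would leave the label mismatch in place. The main test and the alpha allocation do not change. The cost is a little more programming, using a method that the SAP already specifies, and possibly slightly less favourable estimates.

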6.5.2 MIDAS

The MIDAS is a retrospective, patient-administered, 5-item questionnaire that measures headache-related disability as lost time due to headache from paid work or school, household work, and non-work activities.

Descriptive Analyses

The table of values and changes from baseline in total, absenteeism, presenteeism, and item scores is provided, and has a similar format as the one described in Section 6.5.1.

Results support exploratory objective #8.

Treatment Group Comparisons

Analyses of each score (total, absenteeism, presenteeism) are based on the DBT efficacy analysis set with scores at both baseline and Week 12 of the DBT outcomes research analysis period.

For each score, treatment groups are compared using a linear regression model with the same attributes as the one described in Section 6.5.1. The table has the same format.

Results for the total score support secondary objective #6, whereas results for the other scores support exploratory objective #8.

